### 10.1.2 Documentation of complications

All such complications as defined in 10.1.1 reported by the patient or observed by the investigator, teacher or therapists will be continuously documented in the designated case report form (Complications form) during the clinical trial/at each follow-up visit.

Patients will be asked using open questions regarding their condition and any untoward medical occurrences during the last four weeks or any unplanned visits to a doctor, ambulance or hospital. In case of an occurrence, causal relationship with the study intervention EYT or Tai Chi, or, for instance in case of patients allocated to standard care alone, with physical training will be assessed.

In case of a potential causal relation to the intervention, the complication has to be documented in the CRF starting from the first administration and until at least 7 days after the last administration of the intervention.

Following information will be documented:

- Characterization of the event
- Onset date, if available
- Severity: see “assessment of severity” (see Section 10.1.3))
- Serious or non-serious
- Action taken with Intervention
- Outcome

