## Synopsis

TITLE OF TRIAL	A multi-centre, parallel-group, randomised controlled trial to assess the efficacy and safety of Eurythmy Therapy and Tai Chi in comparison to standard care alone in chronically ill elderly patients with increased risk of falling
SHORT TITLE	ENTAIER
HEALTH CONDITION STUDIED	Elderly patients with chronic disease and increased risk for falling
OBJECTIVE(S)	
Primary: To compare Eurythmy Therapy (EYT) plus standard care, Tai Chi plus standard care and standard care alone with respect to the risk of falling over a time period of 6 months.
 
Secondary: To compare EYT added to standard care, Tai Chi added to standard care and standard care alone with respect to the number of falls, number of injurious falls, mobility, balance, cognition, mood, quality of life, instrumental activities of daily living, fear of falling, health-care utilization and safety over a time period of 6 and 12 months. To compare EYT, Tai Chi added to standard care and standard care alone with respect to the risk of falling over a time period of 12 months. To compare inner involvement with practices.

TREATMENTS	
Experimental treatment:
 
Intervention 1: EYT exercises twice (week 1-12), later once weekly (week 13-24), in groups, added to standard care (including a brochure with detailed recommendations on fall prevention)
 
Intervention 2: Tai Chi exercises twice (week 1-12), later once weekly (week 13-24), in groups, added to standard care (including a brochure with detailed recommendations on fall prevention)
 
Control treatment: Standard care alone (including a brochure with detailed recommendations on fall prevention)
 
Duration of treatment per patient: 24 weeks (six months)
 
Follow-up per patient: six months

---

 for practical purposes the three groups will be referred to in this trial protocol as EYT, Tai Chi, and standard care also, although standard care is present in all three groups

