#### 6.4 Treatment Phase and Follow-up Assessments

Patients will record falls in a diary. The diaries will be sent to the study site at the end of each month (or up to 7 days later) until month 12. Patients will be interviewed at the end of each month (or up to 10 days later) to rectify missing data and to ascertain details of falls (see section 2.2), injuries and severity (see section 2.3), and complications (see section 10) by study personnel. If the diary is not send, investigator/physician or study personal will contact the patient.

Patients will visit the study site in person for follow-up evaluations at completion of month 3, 6, 12 (+/- 2 or 4 weeks, see Flowchart, section 6.1) for visit 4, 7, 12. The investigator will send a reminder to the patient. If a patient is not able to come for a study visit, every possible effort is made to collect follow-up evaluations. If feasible, follow-up evaluation can also be conducted at patients home. BBS is assessed and questionnaires are filled in by the trial investigator and/or by the study nurse or the patient (see section 2).

Outcomes measures should be conducted, as far as possible, at a consistent time of the day and consistent to medication cycles, particularly in patients with conditions like Parkinson and Multiple sclerosis, who use medications directly influencing mobility and balance.

Attempts should be made to collect all questionnaires for all patients. Particularly the "standard care alone" patients should get special attention by the investigators to reduce loss of follow-up

in this group. However, if the patient declines to complete the questionnaires, this should be documented in the CRF.

Patients should be given sufficient space and time to complete the study questionnaires and all administered questionnaires should be reviewed for completeness. If missing responses are noted, patients should be encouraged to complete any missing responses.

Investigators must not encourage the patient to change responses reported in questionnaires.

Data obtained from assessments done by the investigator or study nurse, as well as data obtained from patient's fall diary and training diary will be filed with the patient's source documents and documented into the eCRF by designated personnel of the study site (e.g. investigator or study nurse). Patient-reported questionnaires will be stored at the patient's source documents and a duplicate sent to the Clinical Trials Unit in Freiburg.

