“Standard care” means: patients will receive a brochure with detailed written evidence-based recommendations to reduce risk of falling, clearly illustrated and prepared to specifically address the age population (*“Gleichgewicht & Kraft – Einführung in die Sturzprävention”* <https://www.bzga.de/infomaterialien/gesundheit-aelterer-menschen/gleichgewicht-und-kraft-einfuehrung-in-die-sturzpraevention/>)). Patients will also be recommended to visit their primary care physician if they have not done so within the last three months, to discuss fall-prevention measures. Besides the guidance of the brochure, primary care physicians have recent evidence-based guidelines on geriatric assessments including fall prevention measures [60], on managing multi-morbidity [61], and polypharmacy [62]. Current guidelines for fall prevention as well as the fall prevention brochure refer to active lifestyle; to specific exercises to improve balance, strength, flexibility, endurance; to medication modification; to safe home environment; to vitamin D supplementation; to safe footwear; to assistive devices; to improving medical conditions, to treat vision impairment, to manage postural hypotension, heart rate and rhythm abnormalities [22, 23]; the fall prevention brochure also provides addresses. Fall prevention

measures will be organized by the primary care doctors (e.g. prescriptions or referrals) or can be conducted by the patients themselves, using the recommendations of the brochure.

Therapists and Tai Chi teacher will receive a refresher training in appreciating, encouraging, non-judgmental communication (see section 9), before commencement of the trial. They also receive written proposals regarding inner attitude and regarding communication in the exercise groups and in challenging situations. In a follow-up internet-based meeting, they have the opportunity to ask questions and get additional advice. They will receive recommendations to support motivation and adherence of patients. This shall help them to encourage patients to participate in group sessions and to regularly exercise at home and to manage challenges of the group situation.

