by the study sites. It also enables the patient for self-help. Neither therapists nor teacher nor study personal is meant to comment, recommend or dissuade on any standard care measures or any other fall prevention measures.

*How:* EYT and Tai Chi will be provided in one-hour group sessions, á 5 ( $\pm$  1) patients. These group sessions start with an appreciating discussion about practicing (see section 9), followed by practicing the exercises and – if appropriate – ending with a resting time (approximately 15 minutes). Patients are instructed to practice at home at a minimum of 20 minutes on 3 non-class days.

*Where:* EYT and Tai Chi will be provided in appropriate rooms: They should be easily accessible with public transportation, if possible, located nearby the patients (e.g. in retirement homes, meeting places of senior citizens, churches, at the study sites, in doctor's facilities or in rooms provided by EYT therapists or Tai Chi teachers). The room should be accessible for those with disabilities, should support the patients to feel comfortable, to exercise freely (size 50-70 m^2, minimum 36 m^2), friendly bright, quiet, without distraction, properly ventilated and heatable, with no cold stone floor. One chair per patient (stable and safe) has to be provided. Restrooms should be easy accessible, on the same floor.

*When:* EYT and Tai Chi will be provided first twice/week (week 1-12) and then once/week (week 13-24). The intensity is higher in the first 12 weeks (twice per week), taking into account the learning curve, and reduced to once per week during the second 12 weeks when individually practicing has become more routine. Participants are instructed to practice exercises at home.

*Tailoring:* Tai Chi and EYT exercises follow the manuals but are individually tailored to the capabilities of the participants. When exercises beyond the manual are used, this will be documented by the EYT therapists or Tai Chi teacher, together with the reason for using them. In case of significant deterioration of health condition or a new diagnosis during month 1-6, affecting safety of the patient and participation in group classes, the EYT therapist or Tai Chi teacher should contact the investigator whether group sessions should be interrupted.

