*How well:* Patients will give feedback at the beginning of each session regarding their adherence to and their experience with practicing at home. Patients will keep training diaries. Patients will visit group sessions. Deviations from the manual will be documented by therapists and teachers.

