## 10 Safety monitoring and reporting

### 10.1 Complications

#### 10.1.1 Definition of complications

Only complications that could arise from the study specific intervention (EYT or Tai Chi or other exercises in the standard care group) will be collected, documented and – in case of serious complications – reported to the Data Monitoring Committee, DMC (details see chapter 10.3 and DMC Charter). A complication in the ENTAiER study is defined as any untoward medical occurrence in a trial patient such as any unfavourable and unintended sign, symptom, or disease that is possibly related to the study intervention. As the (non-pharmacological) intervention (EYT and Tai Chi) is training of musculoskeletal, sensory, concentrative elements, complications can be:

- Injuries caused by falls that happened during exercises in groups or at home.
- Musculoskeletal pain – except aching muscle - (e.g. foot, knee, low back pain, arthritis, joint effusion, reduced joint function), neuralgia, cardiovascular disorders (e.g. dizziness or faintness, symptoms of hypotension or hypertension, syncope, chest pain, cardiac arrhythmia), vertigo, dizziness, fatigue, syncope, dyspnoea, bronchospasm, dyspnoea, neurological cognitive disturbance, confusion, mood alteration, or others.

Not regarded as complications are

- conditions that were already present at the time of informed consent  
aching muscle ('Muskelkater'), which is to be expected.

The expression "related" means, that there is evidence or argument to suggest a reasonable causal relationship between the event and the administration of the intervention, e.g. close temporal connection, exclusion of other causes.

The assessment "not related" is appropriate, if the complication is clearly or most likely explained by other causes even if a potential relationship between treatment and the complication cannot be completely excluded.

Falls and injurious falls will be documented as primary outcomes. In case they happen during exercises in groups or at home, this will be noted. They will also be reported to the study center by therapists or teachers in case that they happen during exercises. Injuries caused by falls that happened during exercises in groups or at home will be documented as complications and indicated as caused by a fall. All falls that happen during exercises in groups or at home will be reported to the DMC with the regular report on complications.

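### Teachers and therapists feed the complications form only in the EYT and Tai Chi arms, and the source of each report is not recorded, so reading complication rates against standard care is open to unequal ascertainment

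*Protocol*

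**What the plan says.** Protocol section 10.1.2 puts on one form the complications "reported by the patient or observed by the investigator, teacher or therapists will be continuously documented in the designated case report form". The sentence goes on to cover both the running course of the trial and each follow-up visit. Section 10.1.1 adds a route for falls: "They will also be reported to the study center by therapists or teachers in case that they happen during exercises".

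Section 8.1 schedules EYT and Tai Chi sessions twice weekly in weeks 1 to 12 and once weekly in weeks 13 to 24. It also states: "Patients will give feedback at the beginning of each session regarding their adherence to and their experience with practicing at home". For standard care it says that "patients will receive a brochure with detailed written evidence-based recommendations to reduce risk of falling", with advice to see the primary care physician. No study teacher or therapist is involved there.

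The route common to all arms is the scheduled contact, by telephone or in person each month (sections 6.1 and 6.4). Section 10.1.2 describes the questioning: "Patients will be asked using open questions regarding their condition and any untoward medical occurrences during the last four weeks", together with unplanned medical visits. For standard care patients, relation to physical training is assessed, so they can have complications too.

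The Synopsis lists, among the comparisons of EYT, Tai Chi and standard care alone, "health-care utilization and safety over a time period of 6 and 12 months". Section 3.1 repeats safety as a three-group objective. Section 14.5.2 plans complication rates with two-sided 95% confidence intervals in the safety population. Section 14.4 defines that population by attendance at one or more group sessions.

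**The concern.** Two arms have an additional observer for harms and the third does not. Many of the complications named in section 10.1.1 are transient, such as dizziness, faintness, fatigue, dyspnoea or a change of mood. A teacher may see such an event as it happens. The same event in a standard care patient who exercises alone reaches the form only if the patient raises it at a later contact or the investigator notices it. If rates per arm are set side by side, part of a difference may reflect who was watching and not what the intervention caused.

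This matters for the protocol's own question of whether EYT and Tai Chi induce harm. It is also hard to repair at the analysis stage: if the reporter is not captured when the event is documented, no later analysis plan can separate the routes.

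**Working it through.** The protocol states no figure for this point, so there is nothing to reproduce. The check sets the routes side by side and counts the occasions.

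**1. Routes by arm**

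| Route | EYT, Tai Chi | Standard care | Protocol section |
|---|---|---|---|
| Open questions at scheduled contacts | yes | yes | 6.1, 6.4, 10.1.2 |
| Observation by the investigator | yes | yes | 10.1.2 |
| FIMA at months 3, 6 and 12 | yes | yes | 10.1.1 |
| Observation by teacher or therapist | yes | no | 8.1, 10.1.2 |
| Teacher or therapist report of exercise falls | yes | no | 10.1.1 |

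**2. Occasions**

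- Group sessions (8.1): 2 × 12 + 1 × 12 = 24 + 12 = 36, in the exercise arms only.
- Scheduled contacts in months 1 to 6 (flowchart, 6.1): 2 telephone + 1 visit + 2 telephone + 1 visit = 6, in every arm.
- Scheduled contacts over 12 months: 6 + 5 telephone + 1 visit = 12, in every arm.

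These counts describe opportunity to observe. They do not measure bias, because a session is not a structured safety query.

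**3. Direction**

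Suppose the true complication risk is equal in two arms. Let *s* be the share of events captured by the routes common to all arms, and *t* the share of the remainder that a teacher or therapist catches. The observed ratio of exercise arm to standard care is

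(s + (1 − s) × t) / s = 1 + t × (1 − s) / s.

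It equals 1 if the common routes miss nothing (s = 1) or the teachers add nothing (t = 0). Otherwise it exceeds 1. The distortion can only raise the apparent rate in the exercise arms.

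**4. Size**

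The protocol gives neither *s* nor *t*, and no expected complication rate. The size therefore cannot be derived.

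**5. Can the routes be separated later?**

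The items that 10.1.2 requires for each event are its characterization, onset date, severity, seriousness, action taken with the intervention, and outcome. The reporter is not among them. On the protocol's own list, the routes are merged at entry.

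**The case against.** The strongest objection is that section 14.5.2 plans no contrast between arms, only rates with confidence intervals. Moreover, the safety population in 14.4, read literally, contains no standard care patients. On that reading there is no planned comparison to distort. This stands as a limit on the claim: the protocol does not specify a biased test. But the Synopsis and section 3.1 make safety a three-group objective, and complications are to be collected in standard care. Once the safety population is reconciled with that objective, rates will be read against each other and the asymmetry remains.

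Second, the common routes are substantial. Monthly open questions, investigator observation and the FIMA run in all arms, and teacher reports distort only what these miss. That is correct, although the FIMA records use of services and will recover few mild events.

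Third, the teacher's role should not be inflated. Section 6.4 lists attendance and manual deviations as what teachers document, and the feedback at the start of each session sits under intervention fidelity in 8.1. That also stands. Section 10.1.2 nevertheless names teachers and therapists as observers of complications.

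Fourth, events in class are genuine, exposure-related harm, and the asymmetry cannot hide harm. Both are true. They argue against restricting the headline rate to the common contacts, but not against recording the source.

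Fifth, tabulation by source could be left to the analysis plan. The table could; the data item could not, because it must be collected with the event.

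A reader might infer two stronger points:

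- **A numerical inflation of the complication rate.** Any figure would rest on assumed capture rates for the monthly interview and for teachers, and the documents supply neither.
- **A distortion of the primary endpoint.** The documents do not support this. Falls come from the daily diary and the monthly interview (2.2, 6.4), no text makes a teacher's report alone an endpoint source, and 10.1.1 already has falls during exercise noted as such.

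**Conclusion.** The point holds as a risk of unequal ascertainment, not as a demonstrated bias. The teacher and therapist route exists in two of three arms, it feeds the same form as patient reports, and the source is not kept. If complication rates are read against standard care, as the objectives invite, the exercise arms may look more harmful than they are. The direction follows from the asymmetry on the assumption that the common routes miss some events and teachers or therapists catch some of these. The size cannot be derived from the protocol.

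The conclusion presupposes that standard care patients enter the safety analysis. Section 14.4 read literally excludes them, which conflicts with the three-group safety objective and with the collection of complications in that arm. That needs its own reconciliation. This is an inexpensive improvement to data capture and presentation, and no analysis of the primary endpoint needs to change.

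**What to change.** 1. **Section 10.1.2:** add a source-of-report item to the list documented for each complication, coded as scheduled interview or visit; teacher or therapist; both.
2. **Section 14.5.2:** keep the all-source complication rate with its 95% confidence interval as the main safety result for each arm. Beside it, present the rate of events elicited at the scheduled contacts common to all arms, labelled as the like-for-like figure against standard care. Show events known only from a teacher or therapist separately for EYT and Tai Chi.
3. **Section 14.4:** reconcile the safety population with the three-group safety objective, since the side-by-side rates need standard care patients in the set.

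All reporting routes, including those to the DMC, stay as they are, and no event is lost from the main result. The cost is one extra eCRF item and one extra table. The item has to be in place when events are documented, because the source may not be recoverable afterwards. The common-contact rate leaves out some genuine in-class events, which is why it should stand beside the all-source rate and not replace it.

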## 6 Study Procedures

### 6.1 Visit schedule and assessments - Flowchart

Table 1 Visit schedule and assessments – Flowchart of the Trial

VISITS	Pre-Treatment (Screening, Waiting time, Baseline/Visit 1 Randomisation)			Treatment					Post-Treatment Follow-up	
					Phone Visit 2-3 (b)	Visit 4 (c)	Phone Visit 5-6	Visit 7 (c)	Phone Visit 8-12 (b)	Last Visit, EOT (d)
TIME		Week -4 to Day -1		Day 0	Month 1 & 2	Month 3	Month 4 & 5	Month 6	Month 7- 11	Month 12
Pre-Screening	X									
Waiting time		X								
Randomization (a)			X							
Informed consent			X							
In-, exclusion criteria			X							
Demographic Data			X							
Handing out Study Book				X						
Fall prevention information				X						
Recommendation to visit primary care doctor				X						
Start treatment or control per patient (e)				X						
Review fall diary					X	X	X	X	X	X
BBS			X			X		X		X
MoCA			X			X		X		X
IADL			X			X		X		X

VISITS	Pre-Treatment (Screening, Waiting time, Baseline/Visit 1 Randomisation)				Treatment					Post-Treatment Follow-up	
						Phone Visit 2-3 (b)	Visit 4 (c)	Phone Visit 5-6	Visit 7 (c)	Phone Visit 8-12 (b)	Last Visit, EOT (d)
Medications			X			X		X		X	
Patient reported: Baseline Questions			X								
Patient reported: Short FES-I			X			X		X		X	
Patient reported: GDS-15			X			X		X		X	
Patient reported: SF-12			X			X		X		X	
Patient reported: ICPH (only EYT and Tai Chi group)						X		X			
Patient reported: FIMA			X			X		X		X	
Safety; complications					X	X	X	X	X	X	
6 month questionnaire								X			

- (a) The randomisation fax should be prepared as close as possible to the treatment.
- (b) Phone visits can be conducted up to +10 days
- (c) Visit 4 and 7 (month 3 and 6) can be conducted within  $\pm 2$  weeks
- (d) Last visit (month 12) can be conducted  $\pm 4$  weeks
- (e) The treatment should start at the same day or one day after but not more than seven days after handing out the study book

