### **Safety assessments**

Safety will be monitored by collecting information on complications at every visit. For details on complications and their collection see section 10.1.

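### The open question on complications looks back four weeks, but contacts are monthly and may be late, so part of the treatment phase is not actively asked about

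*Protocol*

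**What the plan says.** Section 10.1.2 describes how complications are elicited: "Patients will be asked using open questions regarding their condition and any untoward medical occurrences during the last four weeks". The same sentence goes on to ask about unplanned medical visits, and does not make clear whether the four-week limit applies to that item too. The section also requires that complications reported by the patient, or observed by the investigator, teacher or therapist, "will be continuously documented in the designated case report form (Complications form) during the clinical trial/at each follow-up visit". Related complications must be entered from the first administration until at least 7 days after the last.

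On timing, section 6.4 says "Patients will be interviewed at the end of each month (or up to 10 days later"), and its paragraph on safety assessments says "Safety will be monitored by collecting information on complications at every visit". The flowchart notes in section 6.1 give the windows: "Phone visits can be conducted up to +10 days"; "Visit 4 and 7 (month 3 and 6) can be conducted within" 2 weeks either side; "Last visit (month 12) can be conducted" within 4 weeks either side. The flowchart lists complications at the phone visits and at the in-person visits.

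Section 10.1.1 adds that health-care use from the FIMA at months 3, 6 and 12 gives further safety information. Section 14.5.2 reports complication rates with two-sided 95% confidence intervals.

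**The concern.** A recall question at successive contacts gives complete coverage only if it reaches back to the previous contact. Here the look-back is fixed at 28 days, a calendar month is longer, and the permitted windows lengthen some intervals further. A patient who had two days of dizziness just after the last call, and is asked about the last four weeks at a late call, can truthfully answer no.

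The gaps can fall where exposure matters. Sessions normally start on the day the study book is handed over or the day after (section 6.1, note e). A first call at +10 days would then leave out the first, unfamiliar, twice-weekly sessions. Falls are protected by the daily diary, but the protocol describes no comparable daily record for other complications. What is at stake is the completeness of the complication rates, which are the trial's safety endpoint.

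**Working it through.** The plan states no coverage figure, so there is none to reproduce. The check is calendar arithmetic.

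**Inputs**
- Look-back: four weeks = 28 days (10.1.2).
- Nominal interval: one month (6.4). Taken as a calendar month, 365.25/12 = 30.44 days.
- Windows: phone visits 0 to +10 days; visits 4 and 7 ±14 days; last visit ±28 days (6.1).
- Treatment: 24 weeks = 168 days (8.1). Adding the 7 days in 10.1.2 gives 175 days.

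**Formula:** days not covered in an interval = max(0, interval − 28).

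**Contacts on time**
- Per month: 30.44 − 28 = 2.44 days, and 2.44/30.44 = 8.0%.
- Days 0 to 175 contain six such gaps: 6 × 2.44 = 14.6 days, and 14.6/175 = about 8%.
- If sessions start 7 days after the study book (days 7 to 182), the first gap drops out: 5 × 2.44 = 12.2 days, and 12.2/175 = about 7%.

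**Late contacts, previous contact on time**
- Phone visit at +10 days: 30.44 + 10 − 28 = 12.4 days. For the month-1 call these are days 0 to 12.4.
- Visit 4 or 7 at +14 days, if the complication interview moves with the visit: 30.44 + 14 − 28 = 16.4 days. For visit 7 after an on-time month-5 call these are days 152 to 168.6, about the last two weeks of sessions.

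**Compensating intervals:** if the contact after a phone call at +10 days is on time, the interval is 30.44 − 10 = 20.4 days. The look-back then overlaps the previous contact and the gap is 0.

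**Month read as 28 days:** on time, 28 − 28 = 0. Phone visit at +10: 28 + 10 − 28 = 10 days. Visit 4 or 7 at +14: 28 + 14 − 28 = 14 days. This reading removes the on-time gap but not the late ones.

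**Last visit:** with an on-time month-11 call and the last visit at +28 days, 30.44 + 28 − 28 = 30.4 days. This lies far outside the minimum documentation window, which ends at about day 175 to 182.

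**After the change:** with the look-back tied to the last contact, the uncovered time is 0 days whatever the visit timing.

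**The case against.** Five points can be made for the plan as it stands.

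1. **The question is not the only route.** A reader might infer that uncovered days are never asked about and their events are lost. The text does not support that. Section 10.1.2 requires continuous documentation of reported and observed complications. Active-arm patients meet a therapist or teacher twice weekly, then weekly, and sessions open with a talk about practising. Unplanned medical visits are asked about, and the FIMA records health-care use. This stands, but only in part. These routes need the patient to volunteer the event, staff to see it, or care to be sought. Pain, dizziness, fatigue or mood change after home practice may meet none of these conditions.

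2. **Uncovered days are not missed events.** A complication that begins in a gap and lasts into the next 28 days is still caught. This stands: only short-lived events are at risk, and the documents give no figure for their frequency.

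3. **Four weeks may be shorthand for a month.** The Synopsis equates 24 weeks with six months. This makes the on-time 7-8% debatable, but leaves 10 to 14 days when contacts are late.

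4. **The 16-day figure depends on the reading.** Section 6.4 caps the monthly interview at 10 days late and gives the wider windows to the in-person evaluations. On that reading the maximum is about 12 days. The flowchart lists complications at the in-person visits, so the text allows both.

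5. **Serious harm is largely protected.** Section 10.2.2 covers serious complications from the first intervention to at least 7 days after the last, with no recall limit, and falls during exercises go to the Data Monitoring Committee separately. A reader might infer that the committee's view of harm is generally unreliable, or that the arms are biased against each other. Neither is shown, and the recall rule is the same in all arms.

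**Conclusion.** The mismatch is real, modest and confined to the active open question. In the treatment phase it leaves about 2.4 days per calendar month uncovered with on-time contacts (about 7-8% of treatment time, nil if a month means four weeks). It leaves about 12 days before a phone visit at +10 days, and up to about 16 days before visit 4 or 7 at +14 days if the interview moves with the visit. The late-contact figures assume that the previous contact was on time and that the four weeks are applied literally. They describe single intervals at the window limits, not an expected average.

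Complication rates may be somewhat understated. By how much cannot be derived from the protocol, because it depends on how many brief events are neither volunteered, observed nor followed by a medical visit.

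A reader might also give weight to the 30 days that can be lost before a late month-12 visit. That gap matters little: it falls about six months after sessions end, well beyond the minimum documentation window. The windows also allow contacts less than a month apart, where nothing is lost. The point is worth acting on because it concerns the safety endpoint and the remedy is almost free.

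**What to change.** In section 10.1.2, replace the four-week look-back by *since the last study contact*, and at the first call by *since the study book was handed over*. Print the date of the last contact on the interview form, so that the interviewer can state the period to the patient. Make clear that the same period applies to the item on unplanned medical visits. State in section 6.4 whether the complication interview at months 3 and 6 follows the 10-day limit or the visit window.

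The cost is a reworded sentence, a changed prompt and a clarification, with no extra contact or staff. The only downside is a slightly longer recall period when a contact is late.
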